6.4. REFERENCE START DATE AND STUDY DAY

Study Day will be calculated from the reference start date and will be used to show start/stop day of assessments and events.

Reference start date is defined as the day of the first dose of study vaccination, (Day 1 is the day of the first dose of study treatment) and will appear in every listing where an assessment date or event date appears.

- If the date of the event is on or after the reference date, then:

Study Day = (date of event – reference date) + 1.

Document: \\dccar2dnetvnasc01p-lan1.quintiles.net\cp_ops\PROJECTS\Glaxo SmithKline\GSK205480_HAB61752\SAP
Author: PPD Version Number: 1.0
Version Date: 25OCT2022

Template No: CS_TP_BS016 – Revision 7
Effective Date: 01Nov2021

Reference: CS_WI_BS005

- If the date of the event is prior to the reference date, then:

Study Day = (date of event – reference date).

In the situation where the event date is partial or missing, Study Day, and any corresponding durations will appear partial or missing in the listings. Refer to Section 7.1.1 for rules applicable on partially completed dates when used in calculations.

6.4.1. ATTRIBUTING EVENTS TO VACCINE DOSES

The dose relative to an event is the most recent study dose given to a participant prior to the start of a given event. For example, if the start date of an adverse event is between Dose 1 and Dose 2, the relative dose will be Dose 1.

If an event starts on the same day as a study dose, the relative dose will be derived from the additional information provided in the CRF using the contents of the flag indicating if the event occurred before or after vaccination. If ‘after vaccination’ is selected or if the selection is missing, the relative dose for the event will be the one administered on the start day of the event. If ‘before vaccination’ is selected, the relative dose for the event will be the dose prior to this one. Where applicable, the event will be classified as “pre-treatment”.

6.5. BASELINE

Baseline is defined as:

- Day 1 pre-dose for seroresponse calculation (4-fold for Anti-O:2 IgG and $\geq 4.3 \mu\text{g/mL}$ for Anti-Vi Ag IgG antibody concentrations)
- Day 1 and each vaccination pre-dose for immunogenicity within-participant GMR
- Each vaccination pre-dose for hematology, biochemistry and vital signs assessments.

However, if a participant is missing the planned individual vaccination pre-dose result, change from baseline will not be calculated for within-participant GMR, hematology and biochemistry. For hematology and biochemistry, screening value can be used as Day 1 predose if the value at said timepoint is missing.

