⁶If a blood sample has been collected during Screening in the 3 days before the date of first vaccination, another safety blood sample does not need to be collected on Visit 1.

⁷All information needs to be verified at the site during an *ad hoc* Visit. Refer to Section 8.2.2 for details on safety monitoring.

AE=adverse event; eCRF=electronic case report form; SAE=serious adverse event; VACC=vaccination

Note: The double-line border following Day 29 and Day 197 indicates the interim analyses, which will be performed on all data obtained up to Day 29 (28 days after first vaccination in Step 2) and Day 197 (28 days after second vaccination in Step 2). The double-line borders following Day 337 indicate the final analysis in these participants, which will be performed on all data obtained up to Day 337.

● is used to indicate a study procedure that requires documentation in the individual eCRF.

○ is used to indicate a study procedure that does not require documentation in the individual eCRF.

Table 2 **Intervals between study visits**

Interval	Planned Visit interval	Allowed interval range
Visit 1 → Visit 2	7 days	7 days – 10 days
Visit 1 → Visit 3	28 days	28 days – 33 days
Visit 1 → Visit 4	168 days	158 days – 178 days
Visit 4 → Visit 5	7 days	7 days – 10 days
Visit 4 → Reminder phone call 2	3 days	1 day – 3 days
Visit 4 → Visit 6	28 days	28 days – 33 days
Visit 4 → Follow-up safety phone contact	168 days	154 days – 182 days

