8. STUDY ASSESSMENTS AND PROCEDURES

Protocol waivers or exemptions are only permitted, when necessary, for the management of immediate safety concerns for the participant.

Immediate safety concerns should be discussed with the Sponsor as soon as they occur or when the study team becomes aware of them. The purpose of this communication is to determine if the participant(s) should discontinue the study intervention.

Study procedures and their timing are summarised in the SoA (Section 1.3).

All Screening evaluations must be completed, and the results reviewed before confirming that potential participants meet all eligibility criteria.

The Investigator will maintain a log of all participants screened. All relevant information, such as confirmation of eligibility and reasons for Screening failure will be mentioned in this Screening log.

Procedures conducted as part of routine clinical management (e.g. haematologic profiles), and obtained before the participant signed the informed consent form (ICF), may be used for Screening and/or for establishing a clinical baseline (provided the procedure met protocol specified criteria and was performed within the time frame defined in the SoA) (Section 1.3).

The SPM provides the Investigator and site personnel with detailed administrative and technical information that does not impact participant safety.

During special circumstances (e.g., COVID-19 pandemic), if local regulations allow, and quality of study procedures is maintained, participant(s) can be offered remote visits (e.g., telemedicine, home visits) for the collection of biological samples and/or safety data/safety assessment(s)/study intervention administration. These remote visits must be performed by qualified study staff. Refer to the SoA for the timing of these visits. Details of how these visits will be conducted are outlined in the SPM.

The following procedures can be performed remotely/virtually (refer to the [Glossary of terms](#) for the definitions of telemedicine, remote and virtual visits) for the duration of such special circumstances:

- Safety follow-up may be performed by telemedicine, which will use secure video conferences, phone calls, and a web portal and/or mobile application as a way of communicating with the participant and monitoring the participant's progress. In addition, qualified study staff may also identify AEs and report them to the Investigator for evaluation.

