9.4. Statistical analyses

9.4.1. Primary endpoint(s) (Amended, 21 August 2023)

[figure not shown]
Endpoint description	Analysis set	Statistical analysis methods
• Percentage of participants with solicited administration-site events during 7 days after each vaccination, on the days of vaccination and the 6 subsequent days (study intervention administered on Day 1 and Day 169), per study group	Solicited Safety Set	• Number and percentages of participants with at least one, any, and Grade 3 administration-site solicited AEs
• Percentage of participants with solicited systemic events during 7 days after each vaccination, on the days of vaccination and the 6 subsequent days (study intervention administered on Day 1 and Day 169), per study group	Solicited Safety Set	• Number and percentages of participants with at least one, any, and Grade 3 systemic solicited AEs
• Percentage of participants with unsolicited AEs during 28 days after each vaccination, on the days of vaccination and 27 subsequent days (study intervention administered on Day 1 and Day 169), per study group	Unsolicited Safety Set	• Number and percentages of participants with unsolicited AEs
• Percentage of participants with any SAEs from first vaccination until 28 days after second study intervention administration (Day 1 to Day 197), per study group	Exposed Set	• Number and percentages of participants with SAEs
• Percentage of participants with AEs leading to withdrawal from the study or withholding further study intervention administration, from first study intervention administration until 28 days after second study intervention administration (Day 1 to Day 197), per study group	Exposed Set	• Number and percentage of participants with AEs/SAEs leading to withdrawal from the study or withholding further study intervention administration
• Percentage of participants with deviations from normal or baseline t values of haematological, renal, and hepatic panel test results at 7 days after each vaccination Day 8 and Day 176 per study group*	Exposed Set	• Number and percentages of participants having haematological, renal, and hepatic abnormalities

[†]Baseline for post-first vaccination at Day 8 is Day 1 (can also be screening blood draw, if performed within 3 days of first vaccination), and baseline for post-second vaccination at Day 176 is Day 169.

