10.9. Appendix 9: Toxicity grading scale for safety laboratory assessment

Laboratory test	Grade 1	Grade 2	Grade 3	Grade 4
BUN – mg/dL	<23 – 26	>26 – 31	>31	Requires dialysis
Creatinine – mg/dL (female)	>1.1 – 1.7	>1.7 – 2.0	>2.0 – 2.5	>2.5 or requires dialysis
Creatinine – mg/dL (male)	>1.3 – 1.7	>1.7 – 2.0	>2.0 – 2.5	>2.5 or requires dialysis
Eosinophils – cell/mm ³	>500 – 1500	>1500 – 5000	>5000	Hypereosinophilic
Haemoglobin (female) – gm/dL	11.0 – <11.6	9.5 – <11	8.0 – <9.5	<8.0
Haemoglobin (female/male) – change from baseline value – gm/dL	Any decrease – 1.5	>1.5 – 2.0	>2.0 – 5.0	>5.0
Haemoglobin (male) – gm/dL	12.5 – <12.9	10.5 – <12.5	8.5 – <10.5	<8.5
Liver function tests – ALT, AST increase by factor	≥1.1 – 2.5 x ULN	>2.5 – 5.0 x ULN	>5.0 – 10 x ULN	>10 x ULN
Lymphocyte decrease – cell/mm ³	750 - <800	500 - <750	250 - <500	<250
Neutrophil decrease – cell/mm ³	1340	1000 - <1340	500 - <1000	<500
Platelet decrease – cell/mm ³	125 000 – <150 000	100 000 – <125 000	25 000 – <100 000	<25 000
WBC decrease – cell/mm ³	2500 – <3700	1500 – <2500	1000 – <1500	<1000
WBC Increase – cell/mm ³	>10 000 – 15 000	>15 000 – 20 000	>20 000 – 25 000	>25 000

Toxicity Grading scale for safety laboratory test results have been based on the US FDA Guidance for Industry [[U.S. Department of Health and Human Services](#), 2007] and adjusted in consideration of local normal ranges provided by the site. Parameters not included in the FDA grading scales will not be graded; their assessment will be based on laboratory normal ranges and medical judgement.

ALT=alanine aminotransferase; AST=aspartate aminotransferase, BUN=blood urea nitrogen; ULN=upper limit of normal, WBC=white blood cells

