1. INTRODUCTION

This document describes the rules and conventions to be used in the presentation and analysis of safety and immunogenicity data at interim and final analyses for Protocol 205480 (H02_01TP). It describes the data to be summarized and analyzed, including specifics of the statistical analyses to be performed. This statistical analysis plan (SAP) is based on final protocol dated 23 August 2022. In scope of this analysis are all primary and secondary objectives and part of CCI [REDACTED]. The iSRC/SRT analyses and the remaining CCI [REDACTED] will be described in separate documents.

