16.2. SAFETY LABORATORY EVALUATIONS

Laboratory results will be included in the reporting of this study for Hematology and Biochemistry. A list of laboratory assessments to be included in the outputs is included in Appendix 9 of the protocol.

For each group and for each haematology and biochemistry parameter:

- The percentage of participants having hematology and biochemistry results below or above the local laboratory reference ranges versus baseline will be tabulated by treatment, timepoint and step.
- The percentage of participants with hematology and biochemistry results by grade versus baseline (visit 1 for first vaccination, Visit 4 for second vaccination) will be tabulated by treatment, timepoint and step.

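### SAP 6.5 lets a screening laboratory value of any age replace a missing Day 1 baseline where the protocol allows 3 days, and the BUN Grade 1 cell in Appendix 9 is not usable as printed

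*SAP*

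**What the plan says.** **Baseline.** SAP 6.5 takes the pre-dose value at each vaccination as the laboratory baseline. If that value is missing, the default is that "change from baseline will not be calculated for within-participant GMR, hematology and biochemistry". The next sentence makes an exception for haematology and biochemistry at the first dose: the "screening value can be used as Day 1 predose if the value at said timepoint is missing". No age limit is given there or elsewhere in the SAP.

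The protocol's laboratory baseline footnote appears in the Synopsis, Table 3 and section 9.4.1. Baseline for Day 8 is Day 1, and it "can also be screening blood draw, if performed within 3 days of first vaccination". Footnote 6 of the Schedule of Activities uses the same window: the Visit 1 safety sample may be omitted if "a blood sample has been collected during Screening in the 3 days before the date of first vaccination". The screening period itself runs from Day -21 to Day -1.

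The SAP is dated 25 October 2022 and is "based on final protocol dated 23 August 2022". Amendment 2, which added the baseline footnote, is dated 21 August 2023. SAP 3.3 declares no departures from the protocol.

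**BUN.** Appendix 9 (protocol 10.9) prints the BUN bands in mg/dL as <23 – 26 (Grade 1), >26 – 31 (Grade 2) and >31 (Grade 3). The Table 17 footnote says blood urea is converted to BUN for grading. SAP 7.1.2 and 16.2.1 both send laboratory grading to Appendix 9.

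**Use.** SAP 16.2 tabulates results against the local reference ranges versus baseline, and also "The percentage of participants with hematology and biochemistry results by grade versus baseline".

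**The concern.** Laboratory deviation from normal or from baseline at Day 8 and Day 176 is a primary endpoint, and the SAP 16.2 tables report it. If the two documents define the Day 1 baseline differently, the programmer must choose, and the same participant may or may not have a baseline category at Day 8.

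One Appendix 9 row, haemoglobin change, takes its grade directly from the baseline. Its Grade 1 band is "Any decrease – 1.5" g/dL, so any fall at all from an admitted baseline is graded.

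The BUN cell raises a separate question: whether one row of the by-grade table can be produced meaningfully from the scale as it stands.

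**Working it through.** The plan states no figure to reproduce here, so the check compares the rules directly.

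**1. Screening days admitted by each rule.** Under SAP 6.4, study day before the first dose is event date minus reference date, so Day -k is k days before vaccination.
- SAP 6.5: Day -21 to Day -1 = 21 days.
- Protocol: Day -3 to Day -1 = 3 days.
- Disputed: Day -21 to Day -4 = 21 - 3 = 18 days. The oldest admissible baseline is 21 days rather than 3.

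**2. When the rules give different answers.**

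| Day 1 sample | Screening draw | SAP 6.5 | Protocol |
|---|---|---|---|
| Taken | Any | Day 1 | Day 1 |
| Absent | Day -3 to Day -1 | Screening | Screening |
| Absent | Day -21 to Day -4 | Screening | None |

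Planned omission under footnote 6 falls in the second row, where the rules agree. Only the third row conflicts, and it needs an unplanned missing Day 1 sample. The Day 176 comparison is untouched, because the SAP exception concerns Day 1 only and both documents use the Day 169 pre-dose value.

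**3. What follows in the third row.** The SAP gives the participant a baseline, a haemoglobin-change grade at Day 8 if haemoglobin has fallen, and a category in the versus-baseline tables. The protocol gives none of these. Haemoglobin change is 1 of the 13 rows in Appendix 9. One participant is 1/12 = 8.3% of a low-dose vaccine group and 1/24 = 4.2% of a full-dose vaccine group. These are weights per participant, not an estimate of how many are affected.

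**4. Timing.** 25 October 2022 to 21 August 2023 is 300 days, so the SAP predates the footnote.

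**5. BUN under each literal reading.**
- Read as everything up to 26: Grade 1 is ≤26, Grade 2 is >26 to 31, Grade 3 is >31. No value is ungraded (0 of 591 grid values from 1.0 to 60.0 in steps of 0.1). A group of 12 with results would show 12/12 at Grade 1 or above, and shifts from ungraded to Grade 1 are zero by construction.
- Read as below 23 only: every value below 23 is Grade 1, and 23 to 26 has no grade. A rise from 22 to 25 (invented values) would then move from Grade 1 to ungraded.

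Both readings grade every value below 23. Values above 26 keep the same grade under both, so Grade 3 does not depend on the cell.

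**6. Comparison with the other rows.** Six Appendix 9 rows grade an increase: BUN, creatinine (female), creatinine (male), eosinophils, ALT/AST and WBC increase. The other five open Grade 1 with > or ≥; only BUN opens with <.

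**The case against.** **On the baseline.** The strongest reply is that the case is residual. The Day 1 sample is required unless a recent screening draw exists, so the conflict needs a missed sample. That stands, and it limits the size. It is also fair that version lag explains the mismatch and that the normal-range part of the endpoint needs no baseline. Neither puts the limit into the SAP.

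Four stronger readings are tempting but not supported:
- *SAP 6.5 contradicts itself.* Its two sentences read naturally as a general rule and a specific exception with a stated trigger. What is missing is the age limit.
- *The SAP already conflicted with its own source protocol when written.* Neither amendment summary lists a change to footnote 6, so the 3-day window may be older than the SAP. But those summaries list main changes, and the 2022 protocol is not among the documents.
- *Protocol section 8 also imposes the limit.* It allows routine results from before consent as a baseline "provided the procedure met protocol specified criteria and was performed within the time frame defined in the SoA". That time frame includes a 21-day screening period, so it does not establish 3 days.
- *The SAP rule moves participants between haemoglobin grades.* In the disputed case there is no Day 1 value to compare with. The contrast is a grade versus no grade.

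**On BUN.** The sign may be a text-extraction error. The machine-read protocol has others: the footnote dagger on baseline in Table 3 becomes a letter t in section 9.4.1, and neutrophil Grade 1 is a bare 1340. Appendix 9 also says the scale was adjusted to local normal ranges, which does not fit grading every low value. This is why confidence is only moderate and why the source check comes first. It does not make the printed cell programmable.

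**Conclusion.** Both points hold, within limits.

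The baseline mismatch is a definite difference between the current protocol and the only SAP text available (high confidence). It affects the Day 8 comparison alone, and only participants whose Day 1 value is unexpectedly missing and whose screening draw falls on Day -21 to Day -4. How many that will be cannot be derived; it may be none.

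The BUN Grade 1 cell is not usable as printed under either literal reading (moderate confidence, subject to the source file). A reader might infer that no BUN value at all would be ungraded; that is true under only one of the two readings. A reader might also infer that safety holds are compromised. They are not, as far as this cell goes: holding rule 2c uses Grade 3 or above, which the cell does not touch, and the reference-range table does not use the grading scale.

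**What to change.** **SAP 6.5.** Restrict the screening fallback to the protocol's 3-day window. Where no such draw exists, apply the SAP's existing default of no change from baseline. Report the number of participants affected, by group. This costs one sentence and no sampling. The price is that a few participants may have no Day 1 laboratory baseline, and hence no haemoglobin-change grade at Day 8. Their Day 8 results against the local reference ranges are still reported.

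**Appendix 9, BUN Grade 1.** Check the cell against the source file to exclude an extraction error. If it is as printed, the sponsor should reconcile it with the adjacent bands and the site's normal range before the by-grade table is programmed. This is one table cell. No cut-off is proposed here.

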6.6. COMMON CALCULATIONS

For quantitative safety measurements (e.g. vital signs, laboratory parameters), change from baseline will be calculated as:

- Observed Value (after baseline) – Baseline Value

For immunogenicity measurements, fold change from baseline will be calculated as:

Document:	\dccar2dnetvnasc01p-lan1.quintiles.net\cp_ops\PROJECTS\Glaxo SmithKline\GSK205480_HAB61752\SAP		
Author:	PPD	Version Number:	1.0

Template No: CS_TP_BS016 – Revision 7
Effective Date: 01Nov2021

Reference: CS_WI_BS005

- Test Value (after baseline)/Baseline Value

6.7. SOFTWARE VERSIONS

All derivations, statistical analyses, summaries, graphs and listings will be generated using SAS version 9.4 or higher (SAS Institute, Inc., Cary, North Carolina).

7. STATISTICAL CONSIDERATIONS

7.1. MISSING DATA

Missing immunogenicity data will be handled as described in Section 15. Following imputation will be used for statistical calculations (and not for participant listings):

7.1.1. DATES

When partially completed birth dates (i.e., with missing day or month) are used in calculations, the following standard rules will be applied:

- A missing day will be replaced by 15
- A missing day and month will be replaced by June 30th

The following exceptions apply:

- Adverse events start dates with missing day:
 - o If the event starts in the same month as at least one of the study doses, the contents of AE.AESTRTPT (the flag indicating if the event occurred before or after vaccination) will be used to complete the date. If 'after vaccination' is selected or if the selection is missing, the imputed start date will match the first (or only) study dose given during that month. If 'before vaccination' is selected, the imputed date will be one day before the only study dose given during that month.
- Adverse events start dates with missing day and month:
 - o If the event starts in the same year as at least one of the study doses, the contents of AE.AESTRTPT (the flag indicating if the event occurred before or after vaccination) will be used to complete the date. If 'after vaccination' is selected, the imputed start date will match the first (or only) study dose given during that year. If 'before vaccination' is selected, the imputed date will be one day before the first (or only) study dose given during that year.

Document:	\dccar2dnetvnasc01p-lan1.quintiles.net\cp_ops\PROJECTS\Glaxo SmithKline\GSK205480_HAB61752\SAP		
Author:	PPD	Version Number:	1.0

Template No: CS_TP_BS016 – Revision 7
Effective Date: 01Nov2021

Reference: CS_WI_BS005

All other cases of incomplete AE or concomitant medication/vaccination start date will follow the standard rules as outlined in Section 6.4.

7.1.2. LABORATORY DATA

Missing laboratory results will not be replaced. Safety laboratory tests will be graded using Appendix 9 of the study protocol.

7.1.3. ADVERSE EVENTS

Solicited Adverse Events:

Daily recording of solicited adverse events: for diary cards indicating the presence or absence of solicited adverse events, for studies using paper diaries which have questions in the CRF indicating the presence or absence of solicited events the following rules are applicable:

- Denominators for the summary of administration site (or systemic) solicited adverse events will be calculated using the number of participants who respond "Yes" or "No" to the question concerning the occurrence of administration site (or systemic) adverse events.
- When a specific solicited adverse event is marked as having not occurred following a specific vaccination (i.e., SDTM FA.FAOCCUR=N for the specified post-vaccination period for the adverse event in question), all daily measurements will be imputed as Grade 0.
- When a specific solicited adverse event is marked as having occurred following a specific vaccination (i.e., SDTM FA.FAOCCUR=Y for the specified post-vaccination period for the adverse event in question), any missing daily recordings will be given imputed values to allow them to contribute to the 'Any' rows but not to specific grade rows of the solicited adverse event summary tables.
- When the occurrence of a specific solicited adverse event is not present (i.e. SDTM FA.FAOCCUR is neither Y nor N for the specified post-vaccination period for the symptom in question) but the group of solicited adverse events (administration site or systemic) is marked as having occurred (i.e. SDTM FA.FAOCCUR=Y), all missing daily recordings will be given imputed values to allow them to contribute to the 'Any' rows but not to specific grade rows of the solicited adverse event summary tables.

The following table shows how participants contribute to each category for a specific solicited adverse event over the Day X to Day Y post-vaccination period:

Document:	\dccar2dnetvnasc01p-lan1.quintiles.net\cp_ops\PROJECTS\Glaxo SmithKline\GSK205480_HAB61752\SAP		
Author:	PPD	Version Number:	1.0

Template No: CS_TP_BS016 – Revision 7
Effective Date: 01Nov2021

Reference: CS_WI_BS005

Solicited adverse event category	Participants included in the calculation of the numerator
Any	All participants with at least one occurrence of the adverse event at grade 1, grade 2, or grade 3 between Day X and Day Y or with the adverse event marked as present and at least one missing daily recording between Day X and Day Y
Grade 1	All participants with at least one occurrence of the adverse event at grade 1, between Day X and Day Y
Grade 2	All participants with at least one occurrence of the adverse event at grade 2 between Day X and Day Y
Grade 3	All participants with at least one occurrence of the adverse event at grade 3 between Day X and Day Y

Unsolicited adverse events

Unsolicited adverse event summaries are including serious adverse events unless specified otherwise. Missing severity, relationship with study vaccine, and outcome of unsolicited adverse events will not be replaced and will appear as 'UNKNOWN' in all statistical listings.

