10.3.9. Assessment of intensity and toxicity

10.3.9.1. Assessment of intensity

The intensity of the following solicited AEs will be assessed as described:

Table 20 Intensity scales for solicited events in adults

Adult		
Event	Intensity grade	Parameter
Pain at administration site	0	None
	1	Mild: Any pain neither interfering with nor preventing normal everyday activities.
	2	Moderate: Painful when limb is moved and interferes with everyday activities.
	3	Severe: Significant pain at rest. Prevents normal everyday activities.
Redness at administration site		Greatest surface diameter in mm
Swelling at administration site		Greatest surface diameter in mm
Temperature*		Temperature in °C
Headache	0	None
	1	Mild: Headache that is easily tolerated
	2	Moderate: Headache that interferes with normal activity
	3	Severe: Headache that prevents normal activity
Fatigue (tiredness)	0	Normal
	1	Mild: Fatigue that is easily tolerated
	2	Moderate: Fatigue that interferes with normal activity
	3	Severe: Fatigue that prevents normal activity
Myalgia (muscle pain)	0	None
	1	Mild: Myalgia present but does not interfere with activity
	2	Moderate: Myalgia that interferes with normal activity
	3	Severe: Myalgia that prevents normal activity
Arthralgia (joint pain)	0	None
	1	Mild: Arthralgia present but does not interfere with activity
	2	Moderate: Arthralgia that interferes with normal activity
	3	Severe: Arthralgia that prevents normal activity

*Refer to the SoA (Section 1.3) for the definition of fever and the preferred location for temperature measurement.

The maximum intensity of administration site redness/swelling will be scored as follows (based on the US Food & Drug Administration [FDA] grading scale [[U.S. Department of Health and Human Services, 2007](#)]):

Redness/Swelling			
Grade 0 Absent	Grade 1 Mild	Grade 2 Moderate	Grade 3 Severe
<25 mm	≥25 – ≤50 mm	>50 – ≤100 mm	>100 mm

The maximum intensity of fever will be scored as follows (based on the US FDA grading scale [[U.S. Department of Health and Human Services, 2007](#)]):

Fever			
Grade 0 Absent	Grade 1 Mild	Grade 2 Moderate	Grade 3 Severe
<38.0°C	≥38.0°C – <38.5°C	≥38.5°C – <39.0°C	≥39.0°C

The Investigator will assess the maximum intensity that occurred over the duration of the event for all unsolicited AEs (including SAEs) recorded during the study. The assessment will be based on the Investigator's clinical judgement.

The intensity should be assigned to 1 of the following categories:

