7.2.6. COUNTING RULES FOR OCCURRENCES OF SOLICITED ADVERSE EVENTS

When the occurrences of solicited adverse events are summarized, each event recorded as having occurred during a specific period will be counted as only one occurrence regardless of the number of days on which it occurs.

For a given participant and the analysis of solicited symptoms within 7 days post-vaccination, missing or non-evaluable measurements will not be replaced. Therefore, the analysis of the solicited adverse events will include only vaccinated participants for doses with documented safety data (i.e., diary card completed). A diary card is considered complete when it has data recorded for all 7 days post vaccination. More specifically the following rules will be used:

- Participants who documented the absence of a solicited symptom after one dose will be considered not having that symptom after that dose.
- Participants who documented the presence of a solicited symptom and fully or partially recorded daily measurement over the solicited period will be included in the summaries at that dose and classified according to their maximum observed daily recording over the solicited period.
- Participants who documented the presence of a solicited symptom after one dose without having recorded any daily measurement will be assigned the value 'UNKNOWN'.
- Doses without diary cards documented will be excluded.

Document: \\dccar2dnetvnasc01p-lan1.quintiles.net\cp_ops\PROJECTS\Glaxo SmithKline\GSK205480_HAB61752\SAP
Author: PPD Version Number: 1.0
Version Date: 25OCT2022

Template No: CS_TP_BS016 – Revision 7
Effective Date: 01Nov2021

Reference: CS_WI_BS005

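### Applied literally, SAP 7.1.3 would count a recorded fever as Grade 0 in the summary tables when the event is marked not occurred; limit the rule to missing days and say how such records are resolved

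*SAP*

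**What the plan says.** SAP 7.1.3 gives three consecutive rules for daily diary data on solicited events.

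- **Event marked absent.** "When a specific solicited adverse event is marked as having not occurred following a specific vaccination" (FAOCCUR=N), the instruction is that "all daily measurements will be imputed as Grade 0".
- **Event marked present.** Here "any missing daily recordings will be given imputed values to allow them to contribute to the 'Any' rows", but not to the rows for specific grades.
- **Event not marked, but its category marked present.** The treatment is the same, again for missing recordings only.

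SAP 7.2.6 adds a counting rule: "Participants who documented the absence of a solicited symptom after one dose will be considered not having that symptom after that dose". The same section states that "missing or non-evaluable measurements will not be replaced".

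Fever, redness and swelling are graded from measurements. Protocol 10.3.9.1 says "The maximum intensity of fever will be scored as follows" and then gives bands in °C, with Grade 1 starting at 38.0°C. Redness and swelling are banded in mm, with Grade 1 starting at 25 mm. SAP 16.1.3 repeats both scales. Protocol 10.3.3 tells participants to take and record an axillary temperature in the evening.

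**The concern.** A temperature can be on record for a participant whose fever question is answered No. The protocol grades that reading by its value. The SAP bullet for FAOCCUR=N, taken word for word, grades it 0. Its two neighbours say that they concern missing recordings and it does not, so a programmer could reasonably code it as applying to every day.

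The percentages with solicited administration-site and solicited systemic events are the first two primary endpoints (protocol 9.4.1). Under the literal coding, disagreement between the occurrence flag and the measurement can move these percentages only downward. A No overrides an above-threshold value. A Yes with complete recordings that are all below threshold does not count, because the Any row needs either a graded day or a missing day.

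**Working it through.** **1. One record under each rule.** Take FAOCCUR=N for fever, with an evening temperature of 38.5°C recorded on one day and lower values on the others.

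| Rule | Result for that day |
|---|---|
| Protocol 10.3.9.1 (38.5 to below 39.0°C) | Grade 2 |
| SAP 16.1.3 (same band) | Grade 2 |
| SAP 7.1.3, absent bullet, applied to all days | Grade 0 |
| SAP 7.1.3, absent bullet, applied to blank days only | Grade 2 |
| SAP 7.2.6, first bullet | Symptom treated as absent |

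The two readings of 7.1.3 therefore give different counts in the Any row and the Grade 2 row. The numerator definitions in 7.1.3 count a participant with at least one day at the relevant grade and place no FAOCCUR condition on that limb. They fit the blank-days reading.

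**2. Effect of one discordant record.** The participant answered the occurrence question and so stays in the denominator (SAP 7.1.3). That symptom's percentage falls by 1/n. Group sizes are from protocol Table 4, assuming every participant contributes data.

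| n | Groups | 1/n | Exact 95% CI, 0 of n | Exact 95% CI, 1 of n |
|---|---|---|---|---|
| 6 | Step 1a and 1b controls | 16.7 points | 0 to 45.9% | 0.4 to 64.1% |
| 12 | Low-dose groups, Step 2 control | 8.3 points | 0 to 26.5% | 0.2 to 38.5% |
| 24 | Full-dose groups | 4.2 points | 0 to 14.2% | 0.1 to 21.1% |

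Intervals are Clopper-Pearson, the SAP 6.1 method. The percentage with at least one systemic (or administration-site) event falls only if the participant has no other qualifying event in that category.

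**3. How many such records.** The documents give no frequency. If 0 to 5% of participants had one after a dose (an assumption), the expected number per full-dose group per dose would be 0 to 0.05 × 24 = 1.2. At 0% nothing changes.

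**4. The plan's own safety figure.** Protocol Table 14 uses 1 − (1 − p)^n. For n = 12 and p = 15%, 1 − 0.85^12 = 85.8%; for n = 24 and p = 7.5%, 1 − 0.925^24 = 84.6%. Both match the table. It starts from an assumed true rate, so neither it nor the sample size depends on this rule.

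**The case against.** The strongest reply is that the bullet only fills blanks. It sits under the heading Missing Data and speaks of imputing. When an event is marked absent, the usual case is that every daily field is empty, so all of them are filled with Grade 0. The word missing is needed in the other bullets because some days there hold values. This is a fair reading and may well be what was meant. It does not settle the matter: the sentence does not say so, and 7.2.6, which lies outside the missing-data section, also lets documented absence decide.

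A second reply is that data checks would catch the conflict. Protocol 10.1.7 and 10.1.8 require source data verification, quality checking and an explanation of discrepancies between eCRF and source. That may resolve some records. But a paper diary that itself shows No beside 38.5°C, transcribed faithfully, agrees with its source, and no section says which entry then prevails.

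Two further limits stand in full:

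- Only temperature is documented as being recorded by participants generally. Nothing says that a diameter is entered when redness or swelling is marked absent.
- The documents do not show how FAOCCUR is set for measured symptoms, so it cannot be assumed to be an unreviewed participant tick-box.

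A reader might infer that the SAP erases recorded reactogenicity. The documents do not support that. No section states that recorded values are overwritten, and SAP 7.1 keeps imputation out of participant listings. The first interim analysis produces no individual listings, however (SAP 4.3, protocol 9.5.1), so a retained value would not be visible in that output.

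**Conclusion.** The rule is ambiguous for one kind of record: an event marked absent with a recorded value of Grade 1 or higher. If applied as worded, it would misgrade that record in the summary tables for two primary safety endpoints, against the protocol's scale and SAP 16.1.3. Each such record costs the symptom's percentage 16.7, 8.3 or 4.2 points at n = 6, 12 or 24.

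The conclusion assumes literal coding and at least one unresolved discordant record. Neither is established. It would go too far to say that the trial's reactogenicity results are biased downward: the documents establish only the direction of any error under literal coding, not that one will occur. All analyses are descriptive, and no hypothesis test depends on the rule. The case for changing it is that the ambiguity touches primary endpoints in small groups and costs almost nothing to remove.

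**What to change.** In SAP 7.1.3, replace the sentence with: *all missing daily measurements will be imputed as Grade 0; recorded values are graded as recorded.* Then add that a FAOCCUR=N record with a recorded value of Grade 1 or higher is queried against source, and counts as an occurrence if the value is confirmed or the query cannot be resolved. Put the same exception in the first bullet of 7.2.6.

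The cost is a few SAP sentences, one check in the derivation program and any queries that arise. The downside is that a few unresolved transcription errors may be counted as events, which is the conservative direction for safety. If only blank days were ever meant, the imputation wording simply confirms it.
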